Humira® for Subcutaneous Injection

Protocol for Special Investigation

(Long-term treatment for Crohn's Disease patients)

AbbVie GK

Protocol No. P13-170

1. Purpose of the investigation

This special investigation of Humira for Subcutaneous Injection will be conducted to obtain information on the safety (especially profile of malignant tumors and serious infections) and effectiveness in patients with Crohn's disease who are receiving Humira for a long period of time.

2. Target number of patients

(1) Target sample size

A total of 500 patients.

(2) Rationale

The incidence of malignant tumors in clinical studies in CD patients conducted in- and outside Japan prior to the approval of Humira for CD were 1.1% (1/90 patients) and 1.1% (16/1459 patients). Based on these incidences, we plan to investigate 300 patients to detect at least one case of malignant tumor at a probability of 95%, and register 500 patients, since a substantial number of patients will discontinue or withdraw from the investigation.

3. Patients to be investigated

Patients who meet the following criteria at baseline will be evaluated in the investigation:

- (1) Patients with Crohn's disease indicated for Humira treatment with the recommended dosage regimen.
- (2) Patients with no past- or present malignant tumors.
- (3) Patients who are not currently receiving Humira.

4. Number of participating institutions by department

The investigation will be conducted in about 100 eligible institutions.

5. Criteria of participating institutions and investigators

The investigation will be conducted by the institutions and physicians that satisfy the following criteria and have concluded agreements with AbbVie GK. for implementation of the investigation.

(1) Participating institutions

Institutions that satisfy the following criteria will participate in the investigation:

- 1) Institutions that have concluded or will conclude agreement with AbbVie GK. for implementing the all-case investigation of Humira in patients with Crohn's disease
- 2) Institutions where the effectiveness of Humira can be evaluated using Crohn's Disease Activity Index (CDAI) whenever possible.

(2) Participating investigators

Investigators that satisfy the following criteria will participate in the investigation:

- 1) Physicians who have participated in the all-case investigation of Humira in Crohn's disease ^{*1}

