12.1. Assessment period for CDAI, WPAI, CRP and non-intestinal conditions

Time allowance of assessment period with the first administration date of Humira as 1 is as follows:

Assessment period	Time Allowance(Day)
At the first administration	- 1 (scheduled date 1)
Week 4 of administration	15 - 43 (scheduled date 29)
Month 3 of administration	71 - 99 (scheduled date 85)
Month 6 of administration	169 - 197 (scheduled date 183)
Year 1 of administration	337 - 393 (scheduled date 365)
Year 1 and Month 6 of administration	519 - 575 (scheduled date 547)
Year 2 of administration	701 - 757 (scheduled date 729)
Year 2 and Month 6 of administration	883 - 939 (scheduled date 911)
Year 3 of administration	1065 - 1121 (scheduled date 1093)
At final assessment	Final assessment of each patient no matter whether the each assessment period is within Time Allowance.

The data for analysis should derive from the date closest to the scheduled date within Time Allowance. If there are more than one data dated on the same day, select the worst value.

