Note: Follow “12.2 Assessment period for endoscopy results” for Time Allowance of assessment period. The analysis covers only the patients with the data showing that endoscopy for small and large intestines was done on the same day at the first administration and thereafter in the effectiveness analysis group.

“3.2.6.2 Changes in WPAI:CD since the administration was started (Observed Case)”

Patients for analysis: patients in the effectiveness analysis group

Analysis objective: to show WPAI at each assessment period.

Analysis items: Calculate the number of target patients and the summary statistics of WPAI for each assessment period, and conduct a paired-t test which compares the values at the initial administration.

Note: Follow “12.1 Assessment period for CDAI, WPAI, CRP and non-intestinal conditions” for Time Allowance of the final assessment periods. The analysis covers only the patients with the WPAI assessment at the first administration and thereafter in the effectiveness analysis group.

“3.2.7.2 Changes in CRP level since the administration was started (Observed Case)”

Patients for analysis: patients in the effectiveness analysis group

Analysis objective: to show CRP levels at each assessment period.

Analysis items: Calculate the number of target patients and the summary statistics of CRP for each assessment period, and conduct a paired-t test which compares the values at the initial administration.

Note: Follow “12.1 Assessment period for CDAI, WPAI, CRP and non-intestinal conditions” for Time Allowance of the final assessment periods. The analysis covers only the patients with the CRP assessment at the first administration and thereafter in the effectiveness analysis group.

“3.2.7.3 Remission rate at the final assessment in patients who achieved a remission of CDAI at Week 4 of administration”

Patients for analysis: Patients in the effectiveness analysis group (the patients who did not achieve a remission (≥ 150) when the administration was started but achieved the remission (< 150) at Week 4 of administration in CDAI)

Patients for analysis: to show the remission rate of CDAI at the final assessment regarding the patients who did not achieve a remission (≥ 150) when the administration was started but achieved the remission (< 150) at Week 4 of administration.

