Analysis items: calculate the number of target patients, the percentage to the number of patients who achieved a remission at the final assessment and the target patients, and the 95% confidence interval of the remission rate.

Note: The target patients need to have their CDAI measured at 3 time points or more, that is, at the first administration, Week 4 of administration and any point after Week 4 of administration and also have a record that they did not achieve a remission (≥ 150) at the first administration but achieved the remission (< 150) at Week 4 of administration.

Follow “12.1 Assessment period for CDAI, WPAI, CRP and non-intestinal conditions” for Time Allowance of the assessment periods.

For the confidence interval, use the Clopper-Pearson's confidence interval.

“3.2.8 Subsequent changes in the conditions of patients with non-intestinal conditions observed at the first administration (Observed Case)”

Patients for analysis: patients in the effectiveness analysis group

Analysis objective: to show the conditions at each assessment period regarding non-intestinal conditions observed at the first administration.

Analysis item: Calculate the number of target patients, the percentage to the number of patients with the conditions and the number of target patients, and conduct a McNemar test for the first administration per assessment period.

Note: The analysis covers only the patients with the assessment at the first administration and thereafter as well as the patients with symptoms for each “arthritis/arthralgia”, “iritis/uveitis”, and “erythema nodosum/gangrenous abscess/aphthous stomatitis” at the first administration.

To analyze “with any of non-intestinal conditions”, the patients with any symptom at each assessment period regarding any of the items answered as ‘with a symptom’ at the first administration are regarded as the patients with conditions. When a patient had multiple symptoms at the first administration, they should be regarded as “with conditions” if any of the symptoms persisted. Do not include in analysis the items in which no symptoms were observed at the first administration. (Do not include in the analysis a symptom which first developed at an assessment

period after the first administration, either)

Follow “12.1 Assessment period for CDAI, WPAI, CRP and non-intestinal conditions” for Time Allowance of the assessment periods.

“3.4.1 Aggregation for effectiveness per patient background factor (CDAI)”

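### Chart 3.2.7.3 reports remission in Week 4 remitters at an undated last CDAI and leaves out, uncounted, those with no later value, so its percentage refers to no defined length of treatment

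*SAP*

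**What the plan says.** SAP 13.3, chart 3.2.7.3, takes patients in the effectiveness group with CDAI of 150 or more at first administration who "achieved the remission (< 150) at Week 4 of administration in CDAI". The chart's note adds a condition: "The target patients need to have their CDAI measured at 3 time points or more", namely "at the first administration, Week 4 of administration and any point after Week 4 of administration". The result is "the percentage to the number of patients who achieved a remission at the final assessment and the target patients", with a Clopper-Pearson 95% interval.

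SAP 12.1 gives day windows for the scheduled visits but none for the final assessment, which is "Final assessment of each patient no matter whether the each assessment period is within Time Allowance".

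The Protocol's purpose (section 1) includes "effectiveness in patients with Crohn's disease who are receiving Humira for a long period of time", and section 8(1) sets 3 years of observation. CDAI is scheduled from baseline to Year 3 and also when treatment is discontinued (Protocol 8(3), item 9). Reasons for stopping the investigation are recorded (item 13).

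**The concern.** A reader will want this chart to show whether an early remission holds. It reports last known status, at a time that differs between patients and is not shown. Two patients with very different follow-up contribute identically, and Week 4 remitters who left without another CDAI disappear from the denominator with no count and no reason.

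Protocol section 2 expects a substantial number of patients to discontinue or withdraw, and section 8(1) ends the survey for a patient who suspends treatment for 2 months or more. Unequal follow-up is therefore expected. A percentage with an exact interval, placed in a report on long-term treatment, could be read as a statement about long-term remission that the analysis cannot support.

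**Working it through.** The documents give no numerical figure for this chart, so there is none to reproduce. The check is a comparison of sections, followed by two illustrations.

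**1. Timing.** Under SAP 12.1 the Month 3 window is Day 71 to 99 and the Year 3 window is Day 1065 to 1121. A patient whose last CDAI is below 150 in either window adds one to the numerator and one to the denominator. The phrase about any point after Week 4 is not tied to Day 43, the end of the Week 4 window, so a value taken before Month 3 can also be final.

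**2. Other charts.**
- 3.1 and 3.4.1 use the final assessment in the whole effectiveness group.
- 3.2.2.1 and 3.2.2.3 give remission by visit, for all patients and for those not in remission at the start.
- 3.2.1.1 and 3.2.1.2 ask for mean days to the final assessment.

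None is restricted to Week 4 remitters, and 3.2.7.3 does not ask for days to final assessment.

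**3. Size if leaving is unrelated to relapse.** Assumptions: constant relapse rate, relapse not reversed, constant leaving rate, 3 years counted from Week 4, and 40% leaving by Year 3. The 40% is 1 − 300/500, from the sample-size rationale (Protocol 2, SAP 4.3). Applying it to this subgroup is an assumption. It implies 1 − 0.6^(1/6) = 8.2% gone by Month 6 and 1 − 0.6^(1/3) = 15.7% by Year 1.

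Let S be true 3-year maintenance, a = −ln(0.6) = 0.5108 and b = −ln(S). The share in remission at the last assessment is

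a/(a+b) × (1 − 0.6S) + 0.6S.

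| S | b | a/(a+b) | Reported | Relative excess |
|---|---|---|---|---|
| 30% | 1.2040 | 0.2979 | 0.2979 × 0.82 + 0.18 = 42.4% | 41% |
| 50% | 0.6931 | 0.4243 | 0.4243 × 0.70 + 0.30 = 59.7% | 19% |
| 70% | 0.3567 | 0.5888 | 0.5888 × 0.58 + 0.42 = 76.2% | 9% |

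The share of counted remissions with under 1 year of follow-up is a/(a+b) × (1 − (0.6S)^(1/3)) divided by the reported value. This gives 31% at S = 30%, 23% at 50% and 19% at 70%.

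**4. Size if leaving follows relapse.** Keep 40% leaving in total, but let half of relapsers leave 0.1 year after relapse with that CDAI recorded. Simulating 400,000 patients gives about 32%, 55% and 74.5% for true values of 30, 50 and 70%, a relative excess of 6 to 9%. If nearly all leaving follows a recorded relapse, the excess is close to zero.

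**5. What the missing patients leave open.** All counts here are assumed. Take 100 Week 4 remitters, with 80% remission among those seen at Year 3 and 30 to 80% remission at the last visit of those last seen earlier.

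| No later CDAI / last seen early / seen at Year 3 | Chart 3.2.7.3 | Known remission at Year 3, of all 100 (95% CI) |
|---|---|---|
| 5 / 15 / 80 | 68/95 to 76/95 (71.6–80.0%) | 64% (53.8–73.4) |
| 10 / 30 / 60 | 57/90 to 72/90 (63.3–80.0%) | 48% (37.9–58.2) |
| 20 / 40 / 40 | 44/80 to 64/80 (55.0–80.0%) | 32% (23.0–42.1) |

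The last column counts every missing patient as non-remission, so it is a lower bound. The gap of about 8 to 48 percentage points shows how much depends on patients whose timing or absence the chart hides. It is not an estimate of bias.

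**The case against.** **Stated purpose.** The chart is titled and described as remission at the final assessment. The SAP nowhere calls it a durability, maintenance or 3-year analysis. This stands: the purpose is inferred from the population and from the survey's aim.

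**CDAI at discontinuation.** The windowless definition lets the discontinuation CDAI count as the final value. A Week 4 remitter who stops for lack of effectiveness should therefore have a later CDAI, stay in the denominator and usually count as non-remission. Losing that patient takes a missed assessment. This also stands as the plan's intention, although Protocol 5(1) asks institutions to use CDAI only whenever possible, so gaps are foreseeable.

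**The third measurement.** Without it, a patient with no later value would have Week 4 as the final assessment and be in remission by construction. The requirement is sensible for a last-status rate. What is missing is a count of those it removes.

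**Related output.** Visit-level remission (3.2.2.1, 3.2.2.3), Kaplan-Meier continuation (1.6.3) and reasons for discontinuation (1.7) are planned, so the survey does not rest on one undated number. None of these follows the Week 4 remitters.

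**Stronger reading.** A reader might infer that the chart must overstate 3-year maintenance and drifts towards 100% as more patients leave. The documents do not support that as a general statement. It requires leaving to be largely unrelated to relapse, and recorded relapse at discontinuation works against it.

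**Conclusion.** The point holds as one about interpretation. From the text alone, the percentage and interval in chart 3.2.7.3 belong to no defined length of treatment, and an unknown number of Week 4 remitters is left out without being reported.

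The size of any overstatement is conditional. It is about 6 to 12 percentage points (42, 60 and 76% against 30, 50 and 70%) if leaving is unrelated to relapse, relapse is irreversible, rates are constant and 40% leave by Year 3. It falls towards zero as more leavers have a relapse recorded when they stop. The documents give neither CDAI completeness nor the link between leaving and relapse, so they do not fix where the survey lies in that range.

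This is one descriptive effectiveness chart and does not touch the safety objective. It deserves correction because the remedy is cheap and no other output answers the question.

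**What to change.** Keep the last-status rate in 3.2.7.3, labelled as description. For all Week 4 remitters (CDAI 150 or more at the start, below 150 at Week 4), without the third-measurement requirement, add:

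1. The remission rate with Clopper-Pearson 95% interval at each later SAP 12.1 visit to Year 3, or at least at Years 1, 2 and 3, with the numbers observed and missing at each.
2. A sensitivity row that draws on all Week 4 remitters and counts as non-remission those who had discontinued for lack of effectiveness, with the handling of other missing patients stated.
3. A sensitivity row with all Week 4 remitters in the denominator and every missing value counted as non-remission.
4. The number with no CDAI after Week 4, by reason for discontinuation.
5. The distribution of days to final assessment. Chart 3.2.1.1 already asks for the mean.

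Dropping the third-measurement requirement leaves the observed rates in item 1 unchanged. It affects the missing counts and the sensitivity rows.

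A Kaplan-Meier curve of time to first CDAI of 150 or more, or stopping for lack of effectiveness, may be added as supportive. It should be labelled as a stricter endpoint, because one transient rise counts as permanent loss, and as one that assumes uninformative censoring. Patients censored at Week 4 add no follow-up to it.

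The cost is SAP wording and a few table rows from data already collected. The added figures will probably be less favourable than the last-status rate.
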